## 6 TRIAL PARTICIPANT DISPOSITION

### 6.1 Study Screening, Enrollment and Randomization

From the total number of prospective participants screened, the following will be reported:

- Total number of prospective participants screened
- Number and percentage of participants according to their Eligibility Status at Step 1 randomization (eligible and enrolled, eligible not enrolled, ineligible, incomplete screening, ineligible but enrolled).
- Among those participants with eligibility status at Step 1 randomization “Eligible/Not Enrolled” or “Ineligible”, the number and percentage of participants according to the reasons for ineligibility or not enrollment.
- The number and percentage of participants for whom Step 1 randomization was performed, according to the randomization method employed (online randomization or envelope randomization).

From the total of participants randomized at Step 2, the following will be reported overall and by Step 1 randomization groups (participants assigned to receive the study vaccine at 9 months of age and participants assigned to receive the study vaccine at 15 months of age):

- Number of participants according to their Step 2 randomization assignment

- Number and percentage of participants according to their Eligibility Status at Step 2
- Among those participants with eligibility status at Step 2 randomization “Eligible/Not Enrolled” or “Ineligible”, the number and percentage of participants according to the reasons for ineligibility or not enrollment.
- The number and percentage for whom Step 2 randomization was performed, according to the randomization method employed (online randomization or envelope randomization).

## **6.2 Vaccine Administration**

### **6.2.1 Administration of Randomized Study Meningococcal Vaccine**

Among participants randomly assigned to one of the two study products (NmCV-5 or MenACWY-TT) at Step 2 randomization, the number and proportion of participants that received the vaccine will be reported, as collected in the Meningococcal Vaccine eCRF. The age at the time of vaccination (months) will be summarized (Mean, SD, Median, IQR and Range) along with the age category at the time of vaccination. Among participants for whom the meningococcal vaccine was missed, the primary reason, as collected in the Missed Study Product Administration – Meningococcal eCRF, will be tabulated as number and percentage of participants.

This information will be presented for participants in Group 1 and Group 2 randomly assigned to a study product, overall and by vaccine arm.

### **6.2.2 Administration of EPI Measles-Rubella and Yellow Fever Vaccines**

Administration of EPI vaccines was intended for all participants enrolled in the study, this is, all those for whom Step 1 randomization was performed. The EPI scheduled vaccines include (i) the measles-rubella (MR) vaccinated administered at 9 months of age, (ii) the measles-rubella (MR) vaccine administered at 15 months of age, and (iii) the yellow fever (YF) vaccine administered at 9 months of age.

Among participants with randomization at Step 1 performed, the number and proportion of participants for whom EPI scheduled vaccines were administered will be reported. Among participants for whom one of the scheduled EPI vaccines was missed, the primary reason, as collected in the Missed Study Product Administration – Measles and Rubella and the Missed Study Product Administration – Yellow Fever eCRFs, will be tabulated as number and percentage of participants.

This information will be presented for participants in Group 1 (overall and by vaccine arm), for participants in Group 2 randomized in Step 2 to study product (overall and by vaccine arm) and for participants in Group 2 not randomized in Step 2 to study product.

### **6.2.3 Administration of Meningococcal Vaccine for participants not fully randomized**

Per the protocol, participants in Group 2 who are not randomized to a study product will be offered a non-randomized meningitis (MenACWY-TT) vaccine, intended to be administered at 15 months of age or later. Among this set of participants, the number and proportion who had the vaccine administered by the study team, the age at the time of vaccination (among those who received it) and reasons for vaccine not being administered by the study team (among those who did not receive it), as collected in the Termination Vaccination Status eCRF, will be reported in the final study report.

## **6.3 Study Termination**

Among participants enrolled (those who completed at least Step 1 randomization), the reasons for study termination will be tabulated, with number and percent of participants. This information will be presented for participants in Group 1 (overall and by vaccine arm), for participants in Group 2 randomized in Step 2 to study product (overall and by vaccine arm) and for participants in Group 2 not randomized in Step 2 to study product.

## **6.4 Retention (Visit Completion)**

The number and proportion of participants expected to complete and who completed each visit (regardless of whether the visit was completed within the allowable visit window) will be tabulated, by study arm. The number and proportion of completed visits that were completed inside the pre-specified visit window and outside the visit window will also be tabulated, by study arm.

## **6.5 Serum Specimen Collection for Primary Endpoint Determination**

The following information, as collected in the “Specimen Collection – Blood” eCRF will be summarized:

- Number and percentage of participants for whom blood specimen was collected. Among participants for whom a specimen was not collected, the reported reasons will be grouped in categories and the number and percentage of participants in each category will be reported.
- The specimen collection method, with the number and percentage of participants for whom the collection was done by venipuncture or heel stick.
- Number and percentage of participants for whom the minimum required volume was obtained. Among participants for whom the minimum required volume was not obtained, the reported reasons will be grouped in categories and the number and percentage of participants in each category will be reported.
- Number and percentage of participants for whom the sample was stored for shipment to the central lab. Among participants for whom the sample was not stored for shipment, the reported reasons will be grouped in categories and the number and percentage of participants in each category will be reported.

## **6.6 Protocol Deviations**

Protocol deviations, as collected in the Protocol Deviations eCRF, will be reported. The number and type of protocol deviations will be tabulated by vaccine arm. A listing with all the recorded protocol deviations will be presented, including the type of protocol deviation, the description of the deviation, the plans and/or actions taken to address the deviation and the plans or/actions taken to prevent future occurrences.

## **7 BASELINE DATA**

For Group 1 and Group 2, baseline characteristics of participants will be described by vaccination arm. For participants in Group 1, the baseline data described in this section was collected at the Screening Visit only. For participants in Group 2, some of the baseline data described here was collected at the Screening Visit and Visit 1 (occurring from 3 to 6 months after the Screening visit). When data from the two visits is reported, it will be reported and identified as “at time of Screening” or “at time of Vaccination”.

### **7.1 Demographics Characteristics**

Summaries of demographic characteristics as collected at baseline, including age at enrollment, sex assigned at birth, ethnicity, and race, will be reported tables by study arm. Summaries for age (months) will include mean and SD, median and number and percentage of participants in age categories (8, 9, 10, 11 months). Summaries for sex, ethnicity and race will include number and percentage of participants reporting each category (noting that for ethnicity and race, participants could report more than one). No statistical tests will be performed.

For DSMB reports, tables of Demographic Characteristics will include all participants fully randomized (Step 1 and Step 2 randomization). For WHO reports tables will be produced for the mITT Analysis Set, the PP Analysis Set and the Baseline Immunogenicity Analysis Set. Reports including durability

immunogenicity endpoints will also include a table for the Durability Immunogenicity Analysis Set. The final study report will also include a table of demographic characteristics for all participants enrolled (completing at least Step 1 randomization), by step 2 randomization (Group 1, Group 2, and not fully randomized).

## **7.2 Anthropometry and Vital Signs**

Summaries of height (cm), weight (kg), body temperature (C), hearth rate (beats/min) and rate of respiration (breaths/min), as collected at baseline, will be presented in a table by vaccine arm. WHO standardized z-scores of length/height-for-age, weight-for-age and weight-for-length/height will be calculated (programmatically) based on participants' age (as calculated from reported date of birth) and reported sex at birth, length/height and weight, and summaries of these z-scores will be also be reported. No statistical tests will be performed.

The length/height-for-weight z-score, as calculated by study site personnel for evaluation of eligibility criteria (z-score > -3.0), will not be reported. However, a thorough review has been conducted to ensure that eligibility based on the site reported z-score was consistent with eligibility based on the calculated z-scores.

For DSMB reports, tables reporting Anthropometry and Vital Signs will include all participants fully randomized (Step 1 and Step 2 randomization). For WHO reports tables will be produced for the mITT Analysis set, the PP Analysis Set and the Baseline Immunogenicity Analysis Set. Reports including durability immunogenicity endpoints will also include a table for the Durability Immunogenicity Analysis Set.

## **7.3 Meningitis Immune response at Baseline**

To evaluate meningitis seroprotective levels at baseline, a descriptive analysis of meningitis rSBA titers at Day 1 (serum specimen collected pre-vaccination) will be conducted. For each of the five serogroups (A, C, W, X, Y), the following descriptive summaries will be tabulated by vaccine arm:

- Geometric Mean Titers (GMT), with 95% confidence intervals.
- Range.
- Number and percentage of participants with rSBA titers  $\geq 8$ .
- Number and percentage of participants with rSBA titers  $\geq 128$ .

These summaries will be provided for the Baseline Immunogenicity Analysis Set.

## **7.4 Medical History**

Conditions and/or events collected in the Medical History eCRF will be coded will be coded by MedDRA for preferred term and corresponding system organ class (SOC). Conditions and/or events collected at baseline will be summarized in tables by vaccine arm. Summaries will include the number and percentage of participants reporting a condition/event by MedDRA/SOC, the number and percentage of participants reporting a gradable condition/event, and among those participants, the maximum severity of the condition/event reported. No statistical tests will be performed.

Reported conditions/events reported as gradable and with severity Grade 1 or higher will be provided in a list, including the description of the medical history condition/event, the severity grade, start date of pre-existing condition/event, if the condition is ongoing (at the time that it was reported) and date that the condition/event ended or was resolved, as collected in the Medical History eCRF.

Tables/listings of Medical History conditions/events at baseline will be produced only for the mITT Analysis Set, and to be included only in reports at the end of the study.

## 7.5 Physical Exam

Physical exam findings, as collected at baseline in the Physical Exam eCRF, will be summarized in tables by study arm. Summaries will include the number and percentage of participants with findings from each specific Body System reported as: (exam) Not done, Normal, Abnormal. This will be reported for all Body Systems (HEENT, neck, lymph nodes, heart/cardiovascular, lung/respiratory, liver, spleen, extremities, neurological, skin, other system finding). No statistical tests will be performed.

Findings reported as “Abnormal” will be reported in a listing, including description or other information specified.

Tables/listings of physical exam findings at baseline will be produced only for the mITT Analysis Set, and to be included only in reports at the end of the study.

## 7.6 Concomitant Medications

Medications collected in the Concomitant Medications eCRF be coded using the most recent version of WHO Drug coding, as per the Safety Management Plan. Concomitant medications reported at baseline will be reported in a listing, including information on indication, start date, date stopped, an indicator of the medication ongoing, the dose units, frequency, and route, and if the medication being taken for a reported AE.

The listing of concomitant medication at baseline will be produced only for the mITT Analysis Set, and to be included only in reports at the end of the study.

## 8 EVALUATION OF IMMUNOGENICITY ENDPOINTS

### 8.1 Considerations for reporting of laboratory assay endpoints

As per the Central Assay Plan (CAP), rSBA titers are calculated by the responsible laboratory as the reciprocal of the serum dilution yielding  $\geq 50\%$  killing compared to the number of viable bacterial cells. The lower limit of quantification (LLOQ) for rSBA assay is 4. Samples with rSBA titers below 4 will be reported by the laboratory as “<4”. In these cases, a value equivalent to half the LLOQ will be imputed for analysis and reporting purposes. Invalid assay results for individual specimen-serogroup assays may also be reported and labeled by the laboratory (labels may include “insufficient”, “contaminated”, “no titer obtained” or “hemolyzed”). For analysis purposes, these observations will be considered as missing.

Similar considerations will be made for the Measles and Rubella IgG ELISA assay and the Yellow Fever Neutralizing Antibody assay. Information on the specific limits of detection/quantification and identification of invalid results will be obtained from CAP and the respective data transfer plans (DTPs).

### 8.2 Primary Immunogenicity Analyses

Objectives:

- To demonstrate that the immune responses to meningococcal serogroups A, C, W, Y and X elicited by one dose of NmCV-5 at 9 months of age are non-inferior to the immune responses to meningococcal serogroups A, C, W and Y, elicited by one dose of MenACWY-TT at 9 months of age, as measured by rabbit serum bactericidal antibody (rSBA) titers at 28 days after vaccination, and when meningococcal vaccines are given concomitantly with routine vaccines.
- To demonstrate that the immune responses to meningococcal serogroups A, C, W, Y and X elicited by one dose of NmCV-5 at 15 months of age are noninferior to the immune responses to meningococcal serogroups A, C, W and Y elicited by one dose of MenACWY-TT at 15 months of age, measured by

rSBA titers at 28 days after vaccination, and when meningococcal vaccines are given concomitantly with routine vaccines.

For each of the group randomized to receive the meningitis vaccine at 9 months of age or 15 months of age, there are two sets of hypotheses of interest related to the primary objectives that will be assessed as follows.

### 8.2.1 Non-inferiority of seroprotection for meningitis serogroups A, C, W and Y

**Hypothesis:** Null hypothesis: The immune response to meningitis serogroup "S" at Day 29 elicited by one dose of NmCV-5 is inferior to the immune response elicited by one dose of MenACWY-TT,  
Alternative hypothesis: The immune response to meningitis serogroup "S" at Day 29 elicited by one dose of NmCV-5 is non-inferior, by a pre-specified margin, to the immune response elicited by one dose of MenACWY-TT, where "S" denotes one of the meningitis serogroups: A, C, W or Y.

**Endpoint:**

- Seroprotective response at Study Day 29 to serogroups A, C, W and Y in the NmCV-5 arm,
- Seroprotective response at Study Day 29 to serogroups A, C, W and Y in the MenACWY-TT arm,

with seroprotective response defined as serogroup specific rSBA antibody titers  $\geq 8$ .

**Strata:** Meningitis vaccination age group: Group 1 (9-11 months) and Group 2 (15-17 months of age).

**Analysis Set(s):** The primary analysis will be conducted on the Per Protocol (PP) Analysis Set, with a secondary analysis conducted on the mITT Analysis Set.

**Approach:** The proportion of infants with a seroprotective response (randomized to NmCV-5 vs. MenACWY-TT) will be calculated for each of the serogroups A, C, W and Y as

$$p_{V,S} = \frac{\sum_{i=1}^{N_V} I(Y_i^{V,S} \geq 8)}{N_V} = \frac{n_{V,S}}{N_V},$$

where V indicates arm (NmCV-5 vs. MenACWY-TT), S indicates serogroup,  $N_V$  is the number of infants in the analysis set randomized to arm V and  $Y_i^{V,S}$  is the rSBA antibody titer to the Sth serogroup for the ith infant in arm V.

NmCV-5 will be deemed non-inferior to MenACWY-TT for serogroup S if the lower limit of the 95% confidence interval for  $p_{NmCV-5,S} - p_{MenACWY-TT,S}$  excludes -0.10.

Confidence Intervals will be calculated using the Miettinen-Nurminen method [1, 2].

**Reporting:** The number ( $n_{V,S}$ ) and proportion ( $p_{V,S}$ ) of participants with seroprotective response will be provided (by arm), along with point and 95% CI estimates of the difference in proportions ( $p_{NmCV-5,S} - p_{MenACWY-TT,S}$ ). Proportions and difference in proportions will be reported as percentages (number of infants per 100), with one decimal place.

**Graphical display:** Point estimates and 95% CIs for  $p_{NmCV-5,S} - p_{MenACWY-TT,S}$  will be displayed graphically in a forest plot, with the non-inferiority margin (expressed as -10%) included as reference.

## 8.2.2 Non-inferiority of seroprotection to meningitis serogroup X

**Hypothesis:** Null hypothesis: The immune response to meningitis serogroup X at Day 29 elicited by one dose of NmCV-5 is inferior to the lowest immune response at Day 29 (among meningitis serogroups A, C, W or Y) elicited by one dose of MenACWY-TT.

Alternative hypothesis: The immune response to meningitis serogroup X at Day 29 elicited by one dose of NmCV-5 is non-inferior, by a pre-specified margin, to the lowest immune response at Day 29 (among meningitis serogroups A, C, W or Y) elicited by one dose of MenACWY-TT.

**Endpoints:**

- Seroprotective response at Study Day 29 to serogroup X in the NmCV-5 arm,
- The minimum of the seroprotective responses at Study Day 29 among serogroups A, C, W and Y in the MenACWY-TT arm,

with seroprotective response defined as serogroup specific rSBA antibody titers  $\geq 8$ .

**Strata:** Meningitis vaccination age group: Group 1 (9-12 months) and Group 2 (15-18 months of age).

**Analysis Set(s):** The primary analysis will be conducted on the Per Protocol (PP) Analysis Set, with a secondary analysis conducted on the mITT Analysis Set.

**Approach:** The proportion of infants in the NmCV-5 arm with seroprotective response to serogroup X ( $p_{NmCV-5, X}$ ) will be compared to the proportion of infants MenACWY-TT arm with the lowest seroprotective response among serogroups A, C, W and Y ( $p_{MenACWY-TT, S}$  for  $S \in (A, C, W, Y)$ ). NmCV-5 serogroup X protection will be deemed non-inferior to the lowest of the MenACWY-TT serogroups A, C, W, Y protection if the lower limit of the 95% confidence interval for  $p_{NmCV-5, X} - \min_{S \in (A, C, W, Y)} p_{MenACWY-TT, S}$  excludes -0.10.

Given the additional uncertainty introduced by identifying of the serogroup with the minimum seroprotective response and the estimation of that minimum proportion, confidence intervals for  $p_{NmCV-5, X} - \min_{S \in (A, C, W, Y)} p_{MenACWY-TT, S}$  will be estimated using the bootstrap technique. Bootstrap resampling will be performed stratifying by vaccine arm and the 95% CI will be estimated as the interval between the 2.5th and 97.5th percentiles of the bootstrap empirical distribution.

**Reporting:** The number ( $n_{NmCV-5, X}$ ) and proportion ( $p_{NmCV-5, X}$ ) of participants with seroprotective response to serogroup X in the NmCV-5 arm, along with point and 95% CI estimates for  $p_{NmCV-5, X} - \min_{S \in (A, C, W, Y)} p_{MenACWY-TT, S}$ .

Proportions and difference in proportions will be reported as percentages (number of infants per 100), with one decimal place.

**Graphical display:** The point estimate and 95% CI for  $p_{NmCV-5, X} - \min_{S \in (A, C, W, Y)} p_{MenACWY-TT, S}$  will be displayed graphically in a forest plot, with the non-inferiority margin (expressed as -10%) included as reference.

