Before the final analysis, protocol deviations may be reviewed to determine which protocol deviations could affect the analysis. The per protocol (PP) analysis set will then be defined. Additional analyses of immunogenicity data may be conducted on the PP analysis set. Some or all of the following exclusions may apply: (i) data from all available visits for subjects found to be ineligible at baseline, (ii) data from all visits subsequent to the protocol deviations that are considered to affect the science (iii) data from any visit that occurs substantially out of window.

Analyses of primary endpoints will be performed using SAS v9.4.

No formal multiple comparison adjustments will be employed for multiple primary or secondary endpoints. Unless otherwise noted, 95% confidence intervals (CIs) will be calculated. Statistical tests of non-inferiority and superiority will be 1-sided.

A SAP will be developed by the IDCRC Statistical and Data Science Unit (SDSU) and SCHARP and finalized prior to data lock, and prior to the main analysis of the primary and secondary endpoints. Unless specified otherwise in the SAP, missing data will not be imputed.

General Approach

Unless otherwise noted in the SAP, continuous variables will be summarized using the following descriptive statistics: mean, standard deviation, median, quartiles (25th and 75th percentiles), maximum and minimum. The frequency and percentages (based on the non-missing sample size) of observed levels will be reported for all categorical measures. Unless otherwise specified in the SAP, geometric means of relevant continuous endpoints will be computed as Williams means.

Analysis of the Co-Primary Immunogenicity Endpoint(s)

Analysis of the co-primary immunogenicity endpoints will be conducted for the Immunogenicity Analysis Set. In each arm, the proportion of participants with vaccine seroprotective response, defined as post-vaccination rSBA titers ≥ 8 at Day 29, will be calculated for all serogroups. The

difference in proportions will be estimated and 95% CI will be calculated using the Miettinen-Nurminen method.

For serogroup X, the test for non-inferiority will be based on the difference in the proportion of participants with seroprotective response to serogroup X among those randomized to NmCV-5 and the proportion of participants with seroprotective response to the serogroup with the lowest seroprotective response rate among those randomized to MenACWY-TT.

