## 2.6 Sample Size and Power

Table 3 shows power to test the non-inferiority of the seroprotective response to each of the serogroups A, C, W and Y elicited by the NmCV-5 vaccine, relative to the seroprotective response elicited by the MenACWY-TT vaccine, when administered as a single dose at either 9 months of age or 15 months of age. These calculations assume a non-inferiority margin of -10% (-0.1) for a one-sided hypothesis test, with a 2.5% Type I error rate, and using the Miettinen-Nurminen method for estimation of the 95% CI for the difference in proportions [1, 2]. The resulting power correspond to the sample size of at least 183 and 366 evaluable participants in each of the MenACWY-TT and NmCV-5 arms, respectively, where this target sample size results from the following assumptions:

- At least 600 enrolled participants will be randomly assigned to receive the study vaccine at 9 months of age and
- Among those randomized to receive the study vaccine at 15 months of age, at least 600 participants will receive it at the scheduled visit.
- For each vaccination age, participants will be randomly assigned, in a 1:2 ratio, to receive the MenACWY-TT or the NmCV-5 vaccine.
- At least 92.5% of the 600 enrolled and vaccinated participants will be followed up and contribute a sample for assessment at their Day 29 visit.

**Table 3: Power to test non-inferiority of the proportion of participant with seroprotective response at Day 29 for serogroup A, C, W and Y, for a non-inferiority margin of -10% (-0.1) and a sample size of at least 183 and 366 evaluable participants in MenACWY-TT and NmCV-5 arms, respectively.**

Serogroup	Proportion of seroprotective response in MenACWY-TT arm	Difference in proportion of seroprotective response (NmCV-5 – MenACWY-TT)		Power
		Under the Null (H0)	Under the Alternative (H1)	
A	0.95	-0.1	0	99.97%
C	0.95	-0.1	0	99.97%
W	0.90	-0.1	0	97.50%
Y	0.90	-0.1	0	97.50%

Finally, calculation of Power in Table 3 is based on assumed proportions of seroprotective response in the MenACWY-TT arms that are consistent with, if somewhat more conservative than, to those reported in the literature.

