Power calculations were performed computationally, based on the exact distribution of the primary endpoint of interest under the alternative hypothesis. The probability of each combination of outcomes in the active and control arms was obtained under the assumption that they follow independent binomial distributions. The power of the test was calculated as the sum of probabilities of those scenarios where the outcomes meet the non-inferiority criterion. A simulation was also conducted to corroborate the results.

Table 4 shows power to test the non-inferiority of the seroprotective response to serogroup X. Unlike serogroups A, C, W and Y, non-inferiority of the vaccine for serogroup X will be based on the difference in the proportion of participants randomized to receive NmCV-5 with seroprotective response to serogroup X minus the proportion of participants randomized to receive MenACWY-TT with seroprotective response to the serogroup with the lowest proportion of seroprotective response. Thus, for this test, and consistent with our assumptions listed above, we assume that the lowest proportion of seroprotective response in the MenACWY-TT will be 90% or higher.

**Table 4. Power to test non-inferiority of the proportion of participant with seroprotective response at Day 29 for serogroup X, when compared to lowest seroprotective response rate among A, C, W, Y serogroups, with a non-inferiority margin of -10% (-0.1) and a sample size of at least 183 and 366 evaluable participants in MenACWY-TT and NmCV-5 arms, respectively.**

Serogroup	Lowest Proportion of seroprotective response among Serogroups A, C, W, Y in MenACWY-TT arm	Difference in seroprotective response (Serogroup X in NmCV-5 - lowest proportion among Serogroups A, C, W, Y in MenACWY-TT)		Power
		Under the Null (H0)	Under the Alternative (H1)	
X	0.90	-0.1	0	97.50%

Under the assumption that the test statistics used for the five non-inferiority tests described above are independent, the power to declare overall non-inferiority of NmCV-5 relative to MenACWY-TT at a given vaccination age is calculated to be at least 92.6%. We note, however, that this is a conservative assumption and, given the likely correlation between seroprotective response rates among all the serogroups, the overall power may be higher.

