### **3.3.2 Non-inferiority hypothesis tests**

Endpoint specific one-sided non-inferiority hypothesis tests will be conducted under a 2.5% significance level. Each non-inferiority test will be evaluated by calculating a two-sided 95% confidence interval for the difference in proportions of participants with the specific response and comparing the lower bound of the

CI to a non-inferiority margin (otherwise noted, the margin is -0.1 and will be expressed as -10%). No p-values will be reported.

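### The bootstrap test of serogroup X against the lowest control serogroup has a one-sided error of about 6–8% at the plan's own rates, not the stated 2.5%

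*SAP*

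**What the plan says.** SAP 3.3.2 sets the error rate: "Endpoint specific one-sided non-inferiority hypothesis tests will be conducted under a 2.5% significance level", judged by whether the lower limit of a two-sided 95% interval lies above -10%.

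For serogroup X there is no like-for-like comparator. The null hypothesis in SAP 8.2.2 is therefore that the NmCV-5 response is "inferior to the lowest immune response at Day 29 (among meningitis serogroups A, C, W or Y") under MenACWY-TT. The interval for p_X minus the minimum of the four control proportions comes from a bootstrap: "Bootstrap resampling will be performed stratifying by vaccine arm and the 95% CI will be estimated as the interval between the 2.5th and" 97.5th percentiles. The SAP's reason is that selecting and estimating the minimum adds uncertainty. It specifies no bias correction, recentring or multiplicity allowance, and reports no check of the error rate.

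Protocol 9.6 describes the co-primary analysis differently: the "difference in proportions will be estimated and 95% CI will be calculated using the" Miettinen-Nurminen method, with X set against the lowest control serogroup.

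SAP 2.6 gives power for X of 97.50%, on the basis that "we assume that the lowest proportion of seroprotective response in the MenACWY-TT will be 90% or higher".

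**The concern.** Two things go wrong.

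**The direction of the bias.** When control rates are close together, the smallest observed rate tends to lie below the true smallest rate. That flatters X. A percentile bootstrap resamples around the observed data and takes the minimum again, so the bootstrap distribution of the minimum sits lower still. The lower limit of the difference rises again instead of being corrected.

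**The structure of the hypothesis.** X is within 10 points of the lowest serogroup exactly when it is within 10 points of at least one of A, C, W and Y. The null is that X fails against all four. Testing against whichever serogroup came out lowest is therefore a best-of-four test, which needs a multiplicity allowance. The requirement that all five serogroups pass has the opposite structure and needs none, but it does not cover this selection inside the X test.

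Serogroup X is the component MenACWY-TT lacks, and each age group's co-primary claim depends on it. A lenient X test makes the overall claim, and the report to WHO, lenient too.

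**Working it through.** **Inputs**
- Error rate and margin (SAP 2.6): "These calculations assume a non-inferiority margin of -10% (-0.1) for a one-sided hypothesis test, with a 2.5% Type I error rate".
- Sizes (SAP 2.6): "sample size of at least 183 and 366 evaluable participants in each of the MenACWY-TT and NmCV-5 arms, respectively".
- Control rates (SAP Table 3): A and C 0.95; W and Y 0.90, so W and Y tie for lowest.
- Null boundary for X: 0.90 − 0.10 = 0.80.
- Correlation between serogroups: no value is given. Assumed 0 to 0.8 on a latent normal scale.
- Reading of SAP 8.2.2: the minimum is retaken in every resample, as the stated reason for the bootstrap implies.

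**Step 1: reproduce the plan's power.** Power = Σₓ Σᵧ Bin(x; 366, p_X) · Bin(y; 183, p_C) · I{Miettinen-Nurminen Z at −0.10 > 1.96}.
- 0.90 vs 0.90: 97.50%. 0.95 vs 0.95: 99.97%.
- Overall: 0.9997² × 0.9750³ = 0.926.

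All three match the SAP. With one fixed comparator, the error of this test at 0.80 vs 0.90 is 2.7%. The tabulated power for X thus describes a Miettinen-Nurminen test against a single fixed rate. Simulated power of the SAP's bootstrap rule at X = 0.90 is 99.95%.

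**Step 2: size of the shift** (independent serogroups).
- Plan's rates: the observed minimum averages 1.3 points below the true one, and the bootstrap minimum a further 0.6 below that. Total 1.9 points.
- All four at 0.90: 2.3 + 1.0 = 3.3 points.

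Standard error of a single difference: √(0.80·0.20/366 + 0.90·0.10/183) = 0.0305, about 3.05 points. The shifts are about 0.62 and 1.08 standard errors. Roughly, the error is 1 − Φ(1.96 − 0.62) = 9% and 1 − Φ(1.96 − 1.08) = 19%. This is approximate, because a minimum varies less than a single proportion.

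**Step 3: simulate the SAP rule.** Control infants are resampled as whole four-serogroup patterns, with 600 to 1,000 resamples per trial in the runs that record it. Non-inferiority is declared if the 2.5th percentile exceeds −0.10. X lies exactly 10 points below the true lowest rate. Ranges cover several independent runs of 2,000 to 8,000 trials where the number is recorded; the Monte Carlo standard error is about 0.6 points at 8% with 2,000 trials.

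| Control rates (A, C, W, Y) | Correlation | SAP bootstrap |
|---|---|---|
| 0.95, 0.95, 0.90, 0.90 (plan) | 0 | 7.5–8.4% |
| same | 0.3–0.8 | 5.6–6.7% |
| all 0.90 | 0 | 19.5–20.9% |
| all 0.90 | 0.6 | 13.4–14.0% |
| all 0.95 | 0 | 16.0–16.8% |
| all 0.80 | 0 | 23.8% |
| lowest 0.90, next 0.92 | 0 or 0.5 | 3.5–4.5% |
| one clearly lowest (0.90; others 0.95 or 0.98) | 0–0.8 | 2.0–2.9% |

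The protocol's Miettinen-Nurminen interval against the observed lowest, unadjusted, gives 4.0–4.8% at the plan's rates and 6.1–8.4% with all four at 0.90. It is also above 2.5%, but less so than the bootstrap that replaces it.

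**Step 4: the five-serogroup claim.** With only X at its boundary, A, C, W and Y all pass in about 95% of trials at the plan's rates. False overall success is 7.4% (independent) and 6.6% (correlation 0.5). With all four at 0.90 and independent serogroups it is 18.1%.

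**The case against.** The mechanism is not in dispute. The case on the other side concerns how much it matters.

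- **Ties.** The 6–8% depends on W and Y being equal, and these are rounded planning values. With W at 0.90 and Y at 0.93, error falls to 2.6–3.3%. The only comparator rates by serogroup in the documents (Protocol Table 2) are well spread, from 70.3% to 97.3%, although they concern another vaccine and seroresponse rather than titers of at least 8. This stands as a limit on size. But the tie is the plan's own assumption, and a 2-point gap still gives 3.5–4.5%.
- **The larger figures.** About 20–21% needs four tied rates of 0.90 and independent serogroups, while the SAP expects correlation. That is fair: it is one scenario. Nor is it a ceiling, since lower tied rates give 23–26%.
- **Clinical scale.** At the plan's rates with correlation 0.5, false acceptance is 6.6% at 10 points below, 2.9% at 11, 1.5% at 12 and 0.4% at 13. The defect acts like widening the margin by about 1 point, so a grossly inferior X would still fail. This stands, but the stated error rate applies at the margin.
- **Likelihood.** In Malian children, X seroresponse with non-adjuvanted NmCV-5 was 100% (95% CI 97.5–100), far from 80%. That makes a false claim less likely in practice, but does not make the test valid.
- **Cost.** Protocol 9.2 prescribes two-sided 95% intervals for each serogroup, so a wider interval for X conflicts with it. This is correct, and the fix must address it.

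**Conclusion.** The rule in SAP 8.2.2 is wrong as written. It does not hold the one-sided 2.5% error that SAP 3.3.2 sets. At the plan's own rates and sample sizes the error is about 6–8% across latent correlations of 0 to 0.8, more than twice nominal. It reaches about 20–21% when all four control rates are 0.90 and independent, and is near nominal only when one serogroup is lowest by a few points. The bootstrap was adopted to allow for selecting the minimum, but moves the limit the wrong way and does worse than the protocol's method. The error passes almost undiminished into the five-serogroup claim. These results assume that the minimum is retaken in each resample and rest on assumed correlations, since the SAP gives none.

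**What to change.** In SAP 8.2.2, replace the percentile bootstrap with a Miettinen-Nurminen interval for X against the observed-lowest control serogroup at one-sided 0.025/4 = 0.00625, that is, a two-sided 98.75% interval. Declare non-inferiority if its lower limit is above −10%. Because the null is that X fails against all four serogroups, the Bonferroni division bounds the error whatever the correlation. Simulated error is 1.1–1.3% at the plan's rates and 1.9–2.3% with all four at 0.90. Power for X at the plan's rates is about 97–98%, and five-serogroup power is 93.0% (independent) against the stated 92.6%. A max-T bootstrap centred at the null is a possible alternative, but its error should be simulated first.

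Also:
- Align the 95% interval wording in Protocol 9.2 and 9.6 and SAP 3.3.2 for serogroup X.
- Restate SAP Table 4 and Protocol Table 9 for the test actually used.
- Make the change before the unblinded analyses. SAP 3.1 has later changes reported as post hoc.

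The cost is wording in both documents, a few lines of code and some power. If one control serogroup is clearly lowest, power for X falls from about 97.5% to about 92.5–93%. With three rates at 0.95 and one at 0.90, treating the tests as independent, overall power is then about 0.9997³ × 0.975 × 0.925 = 0.901, still at the 90% design target.
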